5 STUDY POPULATION CHARACTERISTICS

5.1 Subject disposition

Due to differences in data format across studies, in order to facilitate summary of subject disposition, the reasons for discontinuation for individual studies will be collapsed as follows for summaries:

| LTFU Category | CRF Reason |
|-------------------|---|
| ADVERSE EVENT | ADVERSE EVENT |
| LACK OF EFFICACY | LACK OF EFFICACY |
| | LOSS OF EFFICACY |
| LOST TO FOLLOW-UP | LOST TO FOLLOW-UP |
| SUBJECT CHOICE | CONSENT WITHDRAWN |
| | WITHDRAWAL OF CONSENT FOR PERSONAL REASONS NOT RELATED TO AES |
| | WITHDRAWAL OF CONSENT FOR PERSONAL REASONS NOT RELATED TO AES OR LACK OF EFFICACY |
| OTHER | PROTOCOL VIOLATION |
| | OTHER REASON |
| | OTHER |

| LTFU Category | CRF Reason |
|----------------------|--|
| MISSING | If subject discontinued the study and the termination CRF is not available |

Only 1 primary reason for discontinuation should have been reported. In the event that more than 1 reason is specified in the clinical database, both reasons will be summarized and a footnote will be added to the summary table to indicate that at least 1 subject is counted for multiple reasons for discontinuation.

An overall summary of disposition will be provided for all enrolled subjects (ie, all subjects who signed informed consent). The following will be summarized:

- The number of subjects in the Safety Analysis Set
- The number of subjects excluded from the Safety Analysis Set
- The number of subjects who have completed the study
- The number of subjects who have discontinued from the study, including the reason for discontinuation. If subject discontinued the study and the termination CRF is not available, the reason for discontinuation will be reported as “MISSING”.

Additionally, an overall summary of disposition will present the following for subjects in the Safety Analysis Set:

- The number of subjects completing the study (final analysis only)
- The overall number of subjects discontinuing and the number of subjects discontinuing by primary reason for discontinuation. If subject discontinued the study and the termination CRF is not available, the reason for discontinuation will be reported as “MISSING”.

Overall subject disposition will also be summarized by geographic region and seizure type for the Safety Analysis Set.

The number of subjects within each geographic region and the number of subjects with each seizure type will be summarized for the Safety Analysis Set.

Kaplan-Meier estimates of the percentage of subjects completing 3, 6, 12, 24, 36, 48, and 60 months of treatment with BRV will be provided. This analysis will be based on the duration of exposure to BRV as defined in Section 3.2.7. Subjects who have permanently discontinued will be analyzed as events on the last day of treatment with study drug; subjects who complete the study will be censored on the last day of treatment with study drug.

The date of first subject in (date of earliest Visit 1), date of last subject out (date of last scheduled or unscheduled visit), number of enrolled subjects, and the number of subjects in each analysis set or seizure type will be summarized overall and by investigator site.

Subjects who transferred sites will be summarized according to their original site.

5.2 Protocol Deviations

The number and percentage of subjects with at least 1 important protocol deviation will be summarized overall and by category of protocol deviation for the Safety Analysis Set.

6 DEMOGRAPHICS AND OTHER BASELINE CHARACTERISTICS

6.1 Demographics

Demographics summaries will be based on demographic data from follow-up studies for subjects who enrolled in a follow-up study that collected demographic data. Otherwise, demographics summaries will be based on demographic data collected in the previous double-blind study.

Age, age category (<17, 17 to <65, and ≥65 years), gender, racial group and overall racial group (see below), body weight (kg), height (cm), body mass index (BMI) (kg/m²), and BMI category (<18.5, 18.5 to <25, 25 to <30, 30 to <40, ≥40) will be summarized for the Safety Analysis Set. Demographic data will be summarized overall and by subgroup for seizure type and geographic region.

Racial group was not collected in a consistent manner across studies. For this reason, racial group will be collapsed as follows for statistical summaries:

- | | |
|---|---|
| • Category | • CRF Racial Group |
| • American Indian/Alaskan Native | • American Indian/Alaskan Native |
| • Asian | • Asian, Asian/Pacific Islander, Indian/Pakistani |
| • Black | • Black, African-American |
| • Native Hawaiian or Other Pacific Islander | • Native Hawaiian or Other Pacific Islander |
| • White | • White, Caucasian, Hispanic |
| • Other/Mixed | • Other, Other/Mixed, Mixed Race |

moreover, the overall racial group will be collapsed as follows for statistical summaries:

| Category | Racial Group from Previous Study |
|-----------------|--|
| White | White, Caucasian, Hispanic |
| Black | Black, African-American |
| Asian | Asian, Native Hawaiian or Other Pacific Islander, Asian/Pacific Islander, Indian/Pakistani |
| Other | American Indian/Alaskan Native, Other, Other/Mixed |

All subjects should be classified into one of the above categories.

Racial group, ethnicity (Hispanic or Latino, Not Hispanic or Latino), and racial subgroup (Indian/Pakistani, Japanese, Other) were not collected in a consistent manner across all studies; these variables will be provided in subject data listings if available in the clinical data from the previous study but will not be summarized.

6.2 Medical and procedure history

6.2.1 Medical history diseases

The summary of medical history will be based on the medical history at the time of entry into the previous study.

The number and percentage of subjects with a medical history condition, including both resolved and ongoing conditions at the time of entry into the previous study, will be summarized overall and by primary MedDRA system organ class (SOC) and preferred term (PT) for the Safety Analysis Set.

6.2.2 Procedure history and concomitant procedures

Medical procedures are not coded and will only be provided in subject data listings.

6.3 History of epilepsy

All of the following are summarized using data collected at the time of entry into the previous studies or from the Baseline Period of the previous studies.

6.3.1 Etiology of epilepsy

The number and percentage of subjects with each type of etiology as specified on the CRF (genetic, congenital, etc) from the previous studies will be summarized for the Efficacy Analysis Sets for POS and PGS. A subject will be counted as having a particular etiology if that etiology was either confirmed or suspected based on the investigator's assessment.

6.3.2 Epileptic seizure profile

The number and percentage of subjects experiencing each seizure type at any time prior to study entry will be summarized for the Efficacy Analysis Sets for POS and PGS. The following seizure types will be summarized: I, IA, IA1 through IA4, IB, IB1, IB2, IC, II, IIA through IIF, III, and IV. A subject with a history of a more specific seizure type will be counted in all higher levels of seizure types (eg, a subject with a history of IB1 seizures will be counted for seizure types I, IB, and IB1).

6.3.3 Classification of epileptic syndrome

The number and percentage of subjects with each epileptic syndrome will be summarized for the Efficacy Analysis Sets for POS and PGS. This summary will include the number and percentage of subjects within the following categories: localization-related epilepsy; idiopathic, symptomatic, and cryptogenic localization-related epilepsy; generalized epilepsy; and idiopathic, symptomatic, and cryptogenic generalized epilepsy.

6.3.4 Focus localization

The number and percentage of subjects with each category of focus localization (unknown, frontal, temporal, parietal, occipital) will be summarized for the Efficacy Analysis Set for POS for subjects from N01252, N01253, and N01254. Subjects may be counted in more than 1 category of focus localization. Focus localization data was not collected in N01193.

6.3.5 History of epileptic seizures

History of epileptic seizures, including the number and percentage of subjects with a history of status epilepticus and quantitative summaries of epilepsy duration, age at onset of first seizure, and percent of life with epilepsy, will be summarized for the Efficacy Analysis Sets for POS and PGS

6.3.6 Seizure types experienced during baseline of the previous study

The number and percentage of subjects experiencing each seizure type during the Baseline Period will be summarized for the Efficacy Analysis Sets for POS and PGS based on the Baseline seizure diary data from the previous studies. The following seizure types will be summarized: I, IA, IB, IC, II, and IIA through IIF, and III as well.

Subjects will be counted for all higher levels of seizure type categories corresponding to the seizure types or seizure sub-types reported on the CRF.

6.4 Medications

Medications recorded on the Concomitant Medications CRF and the Concomitant Medications (AEDs only) CRF will be classified as either AEDs or non-AEDs based on the preferred drug name search criteria, which are documented outside of the SAP.

- The medication is not an AED if it does not meet the search criteria based on preferred drug name, regardless of which CRF is used for reporting the medication. However, further review will be performed for medications that are recorded on the Concomitant Medications (AEDs only) CRF but are not included in the AEDs search criteria;
- For non-benzodiazepine medications, if the medication meets the search criteria for an AED based on preferred drug name, then the medication will be classified as an AED regardless of indication and regardless of which CRF the medication is recorded on;
- **Benzodiazepines (BZD) taken more than once a week (for any indication) will be considered as a concomitant AED.**

After medications are classified as AEDs or non-AEDs, the standard date imputation algorithms for start and stop date of the medication and first dose and last dose of BRV in the study will be applied. If an AED was taken at any time during dosing with BRV, then the AED is classified as a concomitant AED.

6.4.1 Non-AEDs taken at study entry

The number and percentage of subjects taking non-AED medications at study entry for the previous double-blind study will be summarized by WHO-DRL primary therapeutic group (Anatomic Therapeutic Class [ATC] level 1), therapeutic subgroup (ATC level 2), and preferred drug name for the Safety Analysis Set.

6.4.2 Number of previous AEDs

The number and percentage of subjects taking an AED within 5 years and discontinued prior to entry into the previous double-blind study will be summarized by WHO-DRL preferred drug name for the POS and PGS Efficacy Analysis Sets based on the following categorization: 0-1 AEDs, 2-4 AEDs, and ≥ 5 AEDs.

6.4.3 History of previous AED use

The number and percentage of subjects taking an AED within 5 years and discontinued prior to entry into the previous double-blind study will be summarized overall and by WHO-DRL preferred drug name for the POS and PGS Efficacy Analysis Sets.

6.4.4 AEDs taken at study entry

The number and percentage of subjects taking AEDs at study entry for the previous double-blind study will be summarized by WHO-DRL preferred drug name for the POS and PGS Efficacy Analysis Sets.

6.4.5 Concomitant AEDs

A concomitant AED is an AED which was taken during administration of BRV in N01199 study, regardless of the start and stop date of the AED. The number and percentage of subjects taking concomitant AEDs will be summarized by WHO-DRL preferred drug name for the POS and PGS Efficacy Analysis Sets.

7 MEASUREMENTS OF TREATMENT COMPLIANCE

Study drug compliance will not be assessed due to the complexities associated with the calculation and interpretation of study drug compliance for this study. Study drug dosing will be provided in subject data listings.

8 EFFICACY ANALYSES

In general, all study outcomes based on seizure frequency will be summarized for the Efficacy Analysis Set for POS and all study outcomes based on seizure days will be summarized for the Efficacy Analysis Set for PGS.

The derivations of 28-day adjusted seizure frequency and 28-day adjusted seizure days are described in detail in Section 3.8.1.2 and Section 3.8.1.3, respectively.

All summaries of efficacy data are descriptive; no statistical testing will be performed.

8.1 Statistical analyses of secondary efficacy variables

The following variables are summarized for the Efficacy Population for POS.

8.1.1 Partial onset seizure frequency

Twenty-eight day adjusted POS frequency will be summarized with quantitative descriptive statistics for all subjects for the Baseline Period, the On Treatment Period, and by 3-month

time intervals over the On Treatment Period. The summary over the On Treatment Period will include all subjects in the POS Efficacy Analysis Set. Similar summaries will be provided for the full cohort interval and by 3-month time intervals for each exposure duration cohort.

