### **Variables and Assessments:**

The efficacy variables will be assessed by using the seizure count information recorded on the DRC. The subject will be asked to record the date and the number (where possible) of epileptic seizures he/she has experienced. The type of seizure (according to individual description of seizures) will be defined by the Investigator by adding the ILAE codes. The Investigator will also confirm on the DRC the number of seizures of each type experienced by the subject.

The periods considered in the definition of efficacy variables are the following:

- 3-month periods over the Evaluation Period (V1 until the last evaluation visit).

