#### **13.1.3 Statistical Evaluation**

- General considerations:

Summary statistics will consist of frequency tables for categorical variables and descriptive statistics (number of available observations, mean, median, standard deviation, minimum, maximum, 25th and 75th percentiles) for continuous variables.

The periods considered are:

- Evaluation Period (V1 until the last Evaluation Visit)
- Down-Titration Period
- Post-Treatment Period

Efficacy summaries will be created separately for the POS and PGS subpopulations within the efficacy population, and safety summaries will be created for the safety population.

- Baseline:

Baseline, whether efficacy or safety, will always refer to the original prior study pretreatment Baseline value. Baselines created and validated, as part of the prior study SAPs, will be copied and used by this study for all changes from baseline analyses.

- Study entry/disposition:

Subjects will be sufficiently described to enable a clear understanding of the populations and subpopulations and relevant demographics, disease, medical history, current treatment(s), as well as disposition. Historical and Baseline data will be copied from the prior study as required by the SAP.

- Seizure efficacy variables:

Analyses will be based upon the Efficacy Population. Summaries will be over the entire Evaluation Period and by 3-month periods over the Evaluation Period.

- QOLIE-31-P, HADS, EQ-5D, and socio-professional efficacy variables:

Analyses will be based upon the Efficacy Population and summarized by data collection scheduled visits and for the last Evaluation Period assessment during the first 2 years. Data collected after Year 2 are not planned to be summarized.

- Medical resource and indirect cost efficacy variables:

Analyses will be based upon the Efficacy Population and summarized by 3-month periods. Data collected after Year 2 are not planned to be summarized.

- Safety variables:

Analyses will be based upon the Safety Population. Summary tables will be presented over the Evaluation Period by time windows, by periods, and by categories of total duration of exposure.

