2.2.2 Efficacy variables

2.2.2.1 Secondary efficacy variables

For subjects with focal-onset epilepsy:

- POS (type I) frequency per 28 days during the Evaluation Period
- Percent reduction in POS (type I) frequency per 28 days from Baseline of the previous study to the Evaluation Period
- Responder rate for POS (type I) frequency over the Evaluation Period. A responder is defined as a subject with a $\geq 50\%$ reduction in seizure frequency from the Baseline Period of the previous study

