2.2.2.2 Other efficacy variables

For subjects with focal-onset epilepsy:

- Percentage of subjects continuously seizure-free for all seizure types (I+II+III) for at least 6 months and at least 12 months during the Evaluation Period

For subjects with generalized epilepsy:

- Generalized (type II) seizure days per 28 days during the Evaluation Period
- Percent reduction in generalized (type II) seizure days per 28 days from Baseline of the previous study to the Evaluation Period
- Responder rate for generalized (type II) seizure days over the Evaluation Period. A responder is defined as a subject with a $\geq 50\%$ reduction in seizure days from the Baseline Period of the previous study
- Percentage of subjects continuously seizure-free for all seizure types (I+II+III) for at least 6 months and at least 12 months during the Evaluation Period

The following will be evaluated separately for subjects with focal-onset epilepsy and subjects with generalized epilepsy:

- Change in Patient Weighted Quality of Life in Epilepsy Questionnaire (QOLIE-31-P) scores from Baseline of the previous study to each assessment for the first 2 years and to the last Evaluation Period assessment during the first 2 years
- EuroQol 5 Dimensions (EQ-5D) questionnaire response for each assessment for the first 2 years for the Evaluation Period and for the last assessment during the first 2 years of the Evaluation Period

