8.1.2 Percent reduction in POS frequency

Percent reduction in POS frequency from Baseline to the On Treatment Period will be calculated as follows, where On Treatment Period Frequency is the 28-day adjusted POS frequency during On Treatment Period and Baseline Period Frequency is the 28-day adjusted POS frequency during the Baseline Period of the previous study.

$$\% \text{ Reduction} = 100 \times \frac{\text{Baseline Period Frequency} - \text{On Treatment Period Frequency}}{\text{Baseline Period Frequency}}$$

A similar calculation applies to each 3-month time interval over the On Treatment Period and for the cohort interval for each exposure duration cohort.

Percent reduction from Baseline for POS frequency will be summarized with quantitative descriptive statistics for the On Treatment Period, and by 3-month time intervals over the On Treatment Period. The summary over the On Treatment Period will include all subjects in the POS Efficacy Analysis Set. Similar summaries will be provided for the full cohort interval and by 3-month time intervals for each exposure duration cohort. Percent reduction from Baseline for POS frequency will be summarized in the same manner by geographic region.

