8.1.3 Responder rate for POS frequency

Responders over the On Treatment Period are defined as subjects with a 50% or greater reduction in 28-day adjusted POS frequency from Baseline to the On Treatment Period. A similar calculation applies to each 3-month time interval over the On Treatment Period and for the cohort interval for each exposure duration cohort.

The number and percentage of responders for POS frequency will be summarized for the On Treatment Period, and by 3-month time intervals over the On Treatment Period. The summary over the On Treatment Period will include all subjects in the POS Efficacy Analysis Set. Similar summaries will be provided over the full cohort interval and by 3-month time intervals for each exposure duration cohort. Responder rates for POS frequency will be summarized in the same manner by geographic region.

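### SAP 8.1.1–8.1.3 compute the seizure outcomes to the last dose, taper included, while the protocol and SAP 3.8.1.2 define them over the Evaluation Period

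*SAP*

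**What the plan says.** Two windows are given for the same variables.

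**Evaluation Period.**
- SAP 2.2.2.1 lists the first secondary variable as "POS (type I) frequency per 28 days during the Evaluation Period". Percent reduction and responder rate are listed over the same period, and protocol 13.1.2 agrees.
- Protocol 13.1.3 says of the seizure variables: "Summaries will be over the entire Evaluation Period and by 3-month periods over the Evaluation Period".
- SAP 3.8.1.2 takes all seizure diary from the Evaluation Period for the frequency calculation. SAP 3.8.1.3 uses the same diary for seizure days.
- SAP 3.5.2 screens subjects into the efficacy sets by diary days up to the end of the Evaluation Period.

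**On Treatment Period.**
- SAP 8.1.1: "Twenty-eight day adjusted POS frequency will be summarized with quantitative descriptive statistics for all subjects for the Baseline Period, the On Treatment Period".
- SAP 8.1.2: "On Treatment Period Frequency is the 28-day adjusted POS frequency during On Treatment Period".
- SAP 8.1.3: "Responders over the On Treatment Period are defined as subjects with a 50% or greater reduction in 28-day adjusted POS frequency from Baseline".
- SAP 8.2.2.1–8.2.2.3 handle seizure days for the PGS set in the same manner as 8.1.

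**Where the windows end.** SAP 3.2.7 equates the On Treatment Period with exposure, from first to last dose, and 3.2.1 takes the last dose from any study period. SAP 3.2.4 ends the Evaluation Period at the EDV for a discontinued subject who enters Down-Titration, and starts Down-Titration the next day. The protocol gives only "Evaluation Period (V1 until the last Evaluation Visit", with the same definition in its summary.

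**Seizure freedom.** SAP 2.2.2.2 has "Percentage of subjects continuously seizure-free for all seizure types (I+II+III) for at least 6 months and at least 12 months during the Evaluation Period", whereas 8.2.1.1 looks at the time on BRV treatment.

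**The concern.** For a discontinued subject who tapers, the two windows differ by the whole Down-Titration Period. Taper diary can exist: the protocol dispenses a new Daily Record Card at the EDV (11.2.5), then retrieves it and records seizures at the Final Visit (11.2.7). One programmer working from 3.8.1.2 and another from 8.1.2–8.1.3 could therefore report different frequency, percent-reduction and responder results for such a subject. The same applies to seizure freedom under 2.2.2.2 and 8.2.1.1. Following 8.1 as written does not give the variable that the protocol names.

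Maintenance of efficacy is the only secondary objective, and these are its variables. Seizures during withdrawal of the drug are not what that objective is about.

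**Working it through.** The plan has no sample size, power or alpha figure to reproduce. The check compares the texts and then counts days.

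**1. Does any passage settle the window?**

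| Passage | Points to |
|---|---|
| Protocol 13.1.2–13.1.3; SAP 2.2.2 | Evaluation Period |
| SAP 3.8.1.2, 3.8.1.3 (diary used) | Evaluation Period |
| SAP 8, opening (derivations are in 3.8.1.2 and 3.8.1.3) | Evaluation Period, indirectly |
| SAP 8.1.1–8.1.3; 8.2.2.1–8.2.2.3 by reference | On Treatment Period |
| SAP 8.2.1.1 (seizure freedom) | time on BRV |
| SAP 4.2 | both: it cites 3.2.4 and 3.2.5, then uses diary from while the subject was on BRV |

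The weight favours the Evaluation Period, but no sentence gives it precedence over the 8.1.2 formula or the 8.1.3 definition.

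**2. Length of the taper, T.** Inputs are the weekly steps of at most 50 mg/day and the last week at 20 mg/day (protocol 5.2 and 9.3). At those maximum steps:
- from 50 mg/day: 20, so T = 7 days
- from 100: 50, 20, so T = 14 days
- from 150: 100, 50, 20, so T = 21 days
- from 200: 150, 100, 50, 20, so T = 28 days

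Smaller steps take longer. The 200 mg/day maximum came with Amendment 6 (SAP 2.3), when all subjects had already had their Entry Visit (protocol Table 5:1, footnote l). The 28-day case therefore concerns mainly later intervals.

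**3. Frequency.** If 3.8.1.2 governs, the change is 0%. If taper diary is used, let L be the evaluation days and m the taper seizure rate divided by the on-treatment rate. The documents do not give m; a range of 1 to 3 is assumed. The ratio of the two frequencies is (L + T·m)/(L + T). At m = 1 it is 1; at m = 3:

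| T | L = 90 | L = 360 |
|---|---|---|
| 7 | 111/97 = 1.144 | 381/367 = 1.038 |
| 14 | 132/104 = 1.269 | 402/374 = 1.075 |
| 21 | 153/111 = 1.378 | 423/381 = 1.110 |
| 28 | – | 444/388 = 1.144 |

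With 360 evaluation days and a taper of up to 21 days, the rise is 0–11%. It is larger after early discontinuation and shrinks as exposure lengthens.

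**4. Responders.** A subject who is a responder on the Evaluation Period becomes a non-responder if the reduction is below 1 − 0.5/ratio. At L = 360 and m = 3:
- T = 7: 1 − 0.5/1.038 = 51.8%
- T = 14: 1 − 0.5/1.075 = 53.5%
- T = 21: 1 − 0.5/1.110 = 55.0%

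Only subjects between 50% and these limits change status.

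**5. Seizure freedom.** SAP 8.2.1.1 accepts any continuous interval of the stated length. A longer window can therefore only leave the number of seizure-free subjects unchanged or raise it. The documents give nothing from which to size this.

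**6. Entry to 3-month intervals.** SAP 3.2.5 admits a subject whose last dose is on or after the last day of the interval, given at least one diary day in it. For Months 1–3, a subject qualifies only through taper days if the EDV falls on Day 90 − T to Day 89: Days 83–89, 76–89 or 69–89 for T = 7, 14 or 21. As shares of calendar days these are 7/90 = 8%, 14/90 = 16% and 21/90 = 23%. They are not shares of subjects.

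**The case against.** The strongest reply is that 3.8.1.2 is the only rule that says which diary enters the calculation, 3.8.1.3 adopts it, and Section 8 sends the reader to both. On that reading On Treatment Period in 8.1 is a reporting label. The remark in 4.2 about diary while on BRV could then serve only to exclude drug-free diary. This is a fair argument and makes the Evaluation Period the better reading. It does not dispose of the point, because 8.1.2 puts the other window into a formula and 8.1.3 puts it into a definition.

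Other parts of the case against stand, and limit what can be claimed:
- A reader might infer that the protocol itself ends the Evaluation Period at the EDV. It does not. It says only "Evaluation Period (V1 until the last Evaluation Visit", and Table 5:1 lists the EDV as a visit type of its own. The EDV end date comes from SAP 3.2.4 alone.
- A reader might infer that the rules for interval and cohort entry are also contradictory. They are not: SAP 3.2.5 and 3.2.7 plainly use the last dose, and taper days are exposure. A subject with an EDV on Day 90 would reach the 3-month threshold under either end date. Separate efficacy cohorts would be largely a preference.
- A reader might infer that the efficacy results are materially distorted. That cannot be shown. The taper seizure rate is assumed, the number of subjects dosed after an EDV is not given, and all summaries are descriptive, without testing.

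**Conclusion.** The conflict is real and should be corrected. As written, SAP 8.1.1–8.1.3, and 8.2.2.1–8.2.2.3 by reference, compute the seizure outcomes over a window that is not the one in the protocol or in the SAP's own variable definitions.

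Its reach is limited to descriptive secondary and other efficacy results for subjects dosed after an EDV. The primary safety variables are untouched. The effect on frequency is nil if 3.8.1.2 governs. Otherwise it is the 0–11% rise derived above, for 360 evaluation days and a taper of up to 21 days, and it rests on the assumed rate ratio of 1 to 3 and the documents' maximum taper steps.

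Two smaller gaps belong to the same point. SAP 3.5.2 refers to Section 8 for the end of the Evaluation Period, but the rule is in 3.2.4. And 3.2.4 gives no end date for completed subjects.

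**What to change.** - In SAP 8.1.1–8.1.3, replace On Treatment Period with Evaluation Period, and carry this through to 8.2.2.
- Align the references to time on BRV in 4.2 and 8.2.1.1 with the Evaluation Period.
- In 3.5.2, refer to Section 3.2.4 instead of Section 8.
- In 3.2.4, state an Evaluation Period end date for completed subjects. It should be consistent with protocol 13.1.3 but should not discard on-treatment diary recorded before any taper. The protocol's wording taken literally could drop diary collected after a completer's last full, minimal or yearly evaluation visit.
- Keep last dose for extent of exposure and for adverse events.

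Optional: use the same Evaluation Period end date for entry to the 3-month efficacy intervals in 3.2.5, so that a subject does not count as covering an interval through taper days whose diary is excluded. The exposure cohorts can stay defined by last dose, with a footnote saying so.

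The cost is SAP wording, one corrected cross-reference and one end-date rule. The option adds a derived efficacy end date from existing visit and dosing dates, and the footnote. No new data are needed. The taper lengths used here only measure the gap between the windows; no change to dosing is implied.
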